8.0 DATA SAFETY AND MONITORING

8.1 Data monitoring plan

All patient data will be collected by the Clinical Research Department of Radiation Oncology. All data will be secured in a password protected file with observance of all applicable HIPAA regulation. A data safety monitoring board will meet monthly to evaluate toxicity for this trial. Patients/adverse events will be discussed at these the Radiation Oncology Data Safety monthly meetings. Unexpected serious adverse events will be reported to the IRB and DSMC and minutes of the monthly disease center meetings will be reviewed at the DSMC meetings.

Reports will be submitted annually at the time of the yearly renewal.

All research-related procedures will be conducted by certified medical personnel. The study staff will monitor the subjects closely throughout the study for any adverse events, and subjects will be strongly encouraged to report all issues to the study staff. All supportive measures consistent with optimal patient care will be given throughout the study.

8.2 Stopping criteria

Research subjects will be withdrawn from the study if any one of the following occur:

- 1) Documented neurological worsening following SRS.
- 2) Inability to tolerate SRS prior to surgical resection.
- 3) Multiple seizures following SRS.
- 4) Progression of tumor or radiation/treatment effect at the target site sufficient to necessitate repeat surgical resection or repeat SRS.

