6.2 Ending subject's participation in the study

A subject's participation in the study will be halted if any one of the following would occur:

- Pregnancy test proves to be positive.
- Disease status becomes worse.
- Develop side effects from treatment.
- Physician feels that this preoperative SRS is no longer in your best interest.
- Patient is not compliant with the study.

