7.4.2 Analysis of Secondary Endpoints

1. The patient's overall survival rates for 6 months, 12 months, and 24 months will be analyzed with Kaplan-Meier Survival Curves and the Log-Rank Test.
2. The probability of distant intracranial failure associated with this therapy will be analyzed with Kaplan-Meier Survival Curves and the Log-Rank Test.
3. The analysis of HRQL data will be descriptive. The data will be summarized by question at each time point with the frequency and percentage of each quality level. For each patient, the trajectory of the score will be plotted against time.

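### Sections 6.2 and 8.2 remove worsening patients from the study, with no continued follow-up or censoring rule, so overall survival may read too high and quality of life may mainly describe patients who have not worsened

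*Combined protocol and SAP*

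**What the plan says.** Two lists end a patient's time in the study.

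- Section 8.2: "Research subjects will be withdrawn from the study if any one of the following occur". The triggers include "Documented neurological worsening following SRS", multiple seizures after SRS, and "Progression of tumor or radiation/treatment effect at the target site sufficient to necessitate repeat surgical resection or repeat SRS".
- Section 6.2: a subject's "participation in the study will be halted if any one of the following would occur". The triggers include "Disease status becomes worse" and "Develop side effects from treatment", with no grade, site or cause attached.

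Sections 5.3, 6.3 and 6.5 schedule visits and MRI to 3 years, and 6.3 and 6.5 include the FACT-Br. None of them mentions withdrawn patients. Section 8.4 leaves the way forward to case-by-case decision and speaks of referral for standard care, not study data.

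On analysis, Section 7.4.1 names Kaplan-Meier for local control. Section 7.4.2 says the "overall survival rates for 6 months, 12 months, and 24 months will be analyzed with Kaplan-Meier Survival Curves", uses the same method for distant intracranial failure, and adds: "The analysis of HRQL data will be descriptive". None of these gives a censoring or missing-data rule.

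Sections 4.2.2 and 7.2 treat patients who are not resected after SRS as non-evaluable and replace them, although Section 4.1 sets enrollment at the first day of therapy. No efficacy analysis set is named.

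**The concern.** Both lists are worded as leaving the study, not as stopping treatment, and most of their triggers are plausibly linked to prognosis. Kaplan-Meier needs censoring to be unrelated to prognosis. If patients leave because they worsened, and are censored on that date, the curve assigns them the later survival of patients who did not worsen. HRQL by visit would likewise describe a selected group.

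The lists also differ from each other and fit badly with other sections. Section 3.8 expects new metastases on follow-up scans to be treated, while 6.2 halts participation when disease worsens. Section 8.3 needs the course of a Grade 3 neurologic toxicity to day 60, while 8.2 withdraws the patient for neurological worsening.

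Replacement raises a related question: patients who started SRS and were never resected may drop out of the local-control denominator. The text does not say either way.

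**Working it through.** **1. Do the lists reach past surgery?** Treatment is one SRS fraction with resection 1–7 days later (Sections 3.5, 3.6.2, 3.7). In 8.2, only item 2 is limited to the period before resection. Item 4 refers to *repeat* resection or SRS, so it must apply afterwards, when only follow-up remains to be ended.

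**2. The plan's own figure.** The documents state no OS or HRQL target. The one design figure is N = 24 for local control of 85% against 60%, one-sided 0.05, 80% power, 20% attrition. The normal approximation gives

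n = [(1.645·√(0.6·0.4) + 0.842·√(0.85·0.15)) / 0.25]² = 19.6, so 20.

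Then 20 × 1.2 = 24 (or 20 / 0.8 = 25). The figure reproduces, and the concern does not depend on it.

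**3. OS bias (all inputs assumed).** Take the time to the landmark as 1, with constant hazards: death on study *h*, withdrawal *w*, death after withdrawal *k·h*.

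- True survival: S = e^−(h+w) + ∫₀¹ w·e^−(h+w)u · e^−kh(1−u) du
- Share withdrawn: q = w/(h+w) · (1 − e^−(h+w))
- Kaplan-Meier censored at withdrawal reads e^−h

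Solve for *h* and *w* given S and q. Example with S = 0.50, q = 0.20, k = 2: h = 0.620, w = 0.307. Check: 0.396 alive on study + 0.104 alive after withdrawal = 0.500, and q = 0.307/0.927 × (1 − 0.396) = 0.200. Kaplan-Meier reads e^−0.620 = 0.538.

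| True OS | Withdrawn | k = 1 | k = 2 | k = 3 |
|---|---|---|---|---|
| 30% | 10% | 30.0 | 32.2 | 33.3 |
| 30% | 20% | 30.0 | 34.4 | 36.7 |
| 50% | 5% | 50.0 | 51.0 | 51.6 |
| 50% | 10% | 50.0 | 51.9 | 53.1 |
| 50% | 20% | 50.0 | 53.8 | 56.2 |
| 70% | 10% | 70.0 | 71.3 | 72.3 |
| 70% | 20% | 70.0 | 72.5 | 74.4 |

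**4. Heavier withdrawal.** The 6.2 triggers are ungraded, so larger shares are possible. Use the same model per month with h = 0.03, at 12 months. Kaplan-Meier reads e^−0.36 = 69.8% throughout.

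- w = 0.03 (share withdrawn 0.5 × (1 − e^−0.72) = 26%): true OS is 66.2% for k = 2 and 59.4% for k = 5.
- w = 0.10 (share withdrawn 0.769 × (1 − e^−1.56) = 61%): true OS is 43.4% for k = 5.

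The overstatement runs from about 4 to 26 points. The share alive and still on study, which is the group available for HRQL, is e^−0.72 = 49% in the first case and e^−1.56 = 21% in the second.

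**5. Replacement, worst case.** Count every replaced patient as a failure and use the exact one-sided test against 60%, p = P(X ≥ x | n, 0.60). The smallest passing result at n = 24 is 19.

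| Controlled | 0 replaced (n = 24) | Last passing | First failing |
|---|---|---|---|
| 19 | 0.040 | 19/24, 0.040 | 19/25, 0.074 |
| 20 | 0.013 | 20/25, 0.029 | 20/26, 0.056 |
| 21 | 0.004 | 21/27, 0.042 | 21/28, 0.074 |
| 22 | 0.001 | 22/28 still passes, 0.03 | none with up to four replaced |

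The planned analysis is Kaplan-Meier, so these p-values only illustrate the single-proportion comparison in 7.2.

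**The case against.** The strict reading is not the only one. Several triggers belong to the period before surgery: intolerance of SRS before resection, a positive pregnancy test, and the physician's view that pre-operative SRS is no longer in the patient's interest. Section 8.3 tracks neurologic toxicity and neurologic deaths to day 60, Section 2.2 defines OS with no on-study limit, and the 3-year schedules make no exceptions. The authors may have meant treatment withdrawal only. That is possible, but none of these sections overrides an explicit withdrawal from the study, and item 4 of 8.2 cannot be pre-operative. The consent form was not available for this review and might cover data collection after withdrawal. It would not normally hold a censoring rule.

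The size rests wholly on assumptions, and OS and HRQL are secondary, with no decision threshold. In the 5–20% range the bias is about 1–7 points, below one standard error of a proportion of 50% at n = 24 (√(0.25/24) = 10 points). That stands and limits the weight of the point. A bias does not average out as sampling error does, however, and step 4 shows it can be larger.

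Two further points stand in part. Section 3.8 is an ambiguity rather than a contradiction, since a patient can be off study and still receive standard care. Replacing non-evaluable patients is a stated design choice, and the p-values above are a worst case.

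**Conclusion.** The concern holds and should be fixed. As written, the rules end study participation for events plausibly linked to prognosis, and the protocol neither continues follow-up nor sets a censoring rule.

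- **OS** reads too high if withdrawn patients are censored at withdrawal and die sooner afterwards. With 10–20% withdrawn and a doubled or tripled hazard, a true 30% reads 32–37%, 50% reads 52–56% and 70% reads 71–74%. There is no bias if the hazard is unchanged or deaths after withdrawal are counted.
- **HRQL** would mainly summarise patients who have not worsened.
- **Local control** is affected only if target-site progression is coded as censored, or if patients withdrawn for other reasons would later have failed locally. The documents show no such link.
- **Toxicity**: Section 8.3 attaches no decision rule to DLTs, so its conflict with 8.2 affects reporting only.
- **Replacement** matters only for results near the threshold.

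Confidence is medium, because the withdrawn shares and hazard ratios are assumptions.

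**What to change.** 1. State in 6.2 and 8.2 that these events do not end collection of MRI, HRQL, adverse events and vital status to 3 years unless the patient withdraws consent.
2. Reconcile the two lists with each other and with 3.8 and 8.3, leaving clinical management to the investigators.
3. State the censoring rule for each time-to-event endpoint. Count target-site progression that meets the local-failure definition as an event on its date. That definition must itself be made explicit, since 2.1 compares tumor volumes and 6.4 refers to RECIST on CT.
4. Analyse OS, distant intracranial failure and toxicity in all patients who started SRS.
5. Report replaced patients with reasons. Give local control in all who started SRS alongside the evaluable set, and treat non-resected patients as not controlled in a sensitivity analysis only.

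The cost is protocol and SAP wording plus some added follow-up data, mostly at time points already in the visit schedule. Estimates may become less favourable.

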8.3 Adverse events

Adverse Events will be graded for intensity according to the National Cancer Institute Common Toxicity Criteria, CTCAE Version 4.0. All appropriate treatment areas will have access to a copy of the CTCAE version 4.0. A copy of the CTCAE version 4.0 can be downloaded from the CTEP web site (<http://ctep.cancer.gov>).

The dose limiting toxicity (DLT) will be defined as any adverse event that occurs within 60 days of treatment initiation of radiotherapy and meets any of the following criteria:

Grade 4 or worse or central nervous system necrosis, or cerebral edema, or encephalopathy, or intracranial hemorrhage, or myelitis, or seizure, or stroke, or,

Any other Grade 3 neurologic toxicity which does not improve to grade 2 within 60 days of treatment initiation of radiotherapy, or,

Any neurologic patient death within 60 days of treatment initiation of radiotherapy will be considered a DLT unless in the opinion of the study radiation oncologist and the neurosurgeon, the death is definitely unrelated to treatment or death is definitely related

to disease progression.

There is a theoretical risk that pre-operative SRS could increase the risk of wound healing complications, due to exposure of the scalp to radiation before surgical intervention. However, the dose of radiation to the scalp in these cases is generally less than 1 Gray, so this potential risk is not believed to be a real risk to these patients.

8.4 Assessment of adverse events

Any clinically significant or unexpected disease or condition that is found during the course of this study, will be immediately evaluated by the Principal Investigator and appropriate medical staff and then it will be determined how to proceed with the study/ study treatment.

The subject would likely be referred to the appropriate specialists for standard follow-up medical care.
